3.3.3.3 Repeated-dose toxicity study in cynomolgus monkeys (intramuscular injection)

Toxicity study of 2-week repeated intramuscular injection in cynomolgus monkeys followed by a 2-week recovery period:

During the study, no death or moribundity occurred in the animals of each group; no dosing-related abnormal response was seen during clinical observation. No anaphylactic reaction symptoms occurred in animals during clinical observation after each of the 2 doses. During the study, compared with animals of the same sex in the negative control group in the same period, no obvious change of toxicological significance was noted in various parameters in animals in the low- and high-dose groups (1 dose/animal, 3 doses/animal), including body weight and weight gain, body temperature, ECG waveform and parameters, blood pressure, ophthalmic examination, clinical pathology (blood count, coagulation function, blood biochemistry, and urinalysis), T lymphocyte subsets (CD3⁺, CD4⁺, CD8⁺, and CD4⁺/CD8⁺), serum cytokines (IL-2, IL-4, IL-5, IL-6, TNF- α , and IFN- γ), C-reactive protein, serum complements (C3 and C4), organ weight, organ-to-body ratio, and organ-to-brain ratio.

3.4 Results of Preliminary Clinical Studies

3.4.1 Phase I/II clinical trials on nebulized inhalation

On Apr. 20, 2021, a randomized, double-blind, placebo-controlled phase I/II clinical trial was carried out in Donghai County, Jiangsu to evaluate the safety and immunogenicity of different doses of recombinant COVID-19 vaccine via nebulized inhalation in people aged 18 years and above.

A randomized, double-blind, placebo-controlled design was used for the phase I and phase II trials. In phase I, there were 120 subjects that were divided into 5 groups (low-dose inhalation, medium-dose inhalation, high-dose inhalation, inhalation/intramuscular injection mixed, and single-dose inhalation groups). There were 24 subjects per group and the ratio of the investigational vaccine to the placebo was 3:1. In phase II, there were 720 subjects that were divided into 2 age groups (18–59 years and ≥ 60 years) and there were 6 groups per age group (low-dose inhalation, medium-dose inhalation, high-dose inhalation, inhalation/intramuscular injection mixed, single-dose intramuscular injection, and single-dose inhalation groups). There were 60 subjects per group and the ratio of the investigational vaccine to the placebo was 5:1. An interval of 2 months (56 days) between two doses was used in the mixed nebulized inhalation group.

Preliminary safety data showed:

Overall, there were significantly fewer ARs in the low-, medium-, and high-dose arms of the nebulized inhalation group compared with the intramuscular injection group when a 2-month interval between two doses was used. The safety of the mixed group was particularly pronounced as the total incidence of AR was less than 5% after the second dose.

The preliminary safety data from the phase I trial showed that: During immunization with the first dose, the nebulized inhalation group showed good safety that was similar to the placebo group and better than the intramuscular injection group (i.e., first dose in the mixed group). One grade 3 AR (fever) occurred in the intramuscular injection group. After immunization with the second dose, incidences of ARs in the nebulized inhalation group and the mixed group (second dose: nebulized inhalation) were comparable to the placebo group, and no grade 3 ARs or vaccination-related SAEs occurred.

In the phase II clinical trial, the overall incidence of ARs 14 days after immunization in subjects between 18–59 years old in the two low-dose groups, two medium-dose groups, two high-dose groups, two mixed-dose groups, intramuscular single-dose group, medium single-dose group, and placebo group was 17 (34.00%), 15 (31.25%), 12 (24.00%), 23 (46.00%), 22 (44.00%), 5 (10.00%), and 13 (21.67%), respectively ($P < 0.001$). The incidences of grade 1 ARs in various groups were 16 (32.00%), 13 (27.08%), 10 (20.00%), 21 (42.00%), 21 (42.00%), 5 (10.00%), and 12 (20.00%), respectively ($P = 0.001$); the incidences of grade 2 ARs were 2 (4.00%), 3 (6.25%), 1 (2.00%), 4 (8.00%), 3 (6.00%), 0.00%, and 2 (3.33%), respectively ($P = 0.467$); the incidences of grade 3 ARs were 1 (2.00%), 1 (2.08%), 4 (8.00%), 0.00%, 0.00%, 0.00%, and 0.00%, respectively ($P = 0.015$). Inter-group differences in the incidences of overall ARs, grade 1 ARs, and grade 3 ARs within days 0–14 were statistically significant, while those of grade 2 ARs were not.

In the phase II clinical trial, the overall incidence of ARs 14 days after immunization in subjects aged ≥ 60 years old in the two low-dose groups, two medium-dose groups, two high-dose groups, two mixed-dose groups, intramuscular single-dose group, medium single-dose group, and placebo group was 9 (18.37%), 2 (3.92%), 3 (6.00%), 1 (2.04%), 7 (14.00%), 2 (4.00%), and 5 (8.33%), respectively ($P = 0.026$). The incidences of grade 1 ARs in various groups were 9 (18.37%), 2 (3.92%), 3 (6.00%), 1 (2.04%), 7 (14.00%), 2 (4.00%), and 4 (6.67%), respectively ($P = 0.021$); the incidences of grade 2 ARs were 2 (4.08%), 0.00%, 1 (2.00%), 0.00%, 0.00%, 1 (2.00%), and 1 (1.67%), respectively ($P = 0.544$); no grade 3 or greater ARs occurred. Inter-group differences in the incidences of overall ARs and grade 1 ARs within days 0–14 were statistically significant, while those of grade 2 ARs were not.

According to the preliminary safety observation results in the phase II clinical trial, all dose/immunization procedure groups showed adequate safety profiles. Most ARs were grade 1 reactions and occurred within days 0–7 after each dose. There were few local ARs, and systemic ARs were mainly pyrexia, fatigue, headache, and diarrhea. The incidence of post-immunization ARs among subjects aged 18–59 years was higher than that among subjects aged ≥ 60 years.

Preliminary immunogenicity results showed:

Existing phase I and phase II immunogenicity data were combined for analysis. The 28-day data after 2 doses showed that: the mixed group showed the best result in terms of euvirus neutralizing antibody level, which was around 17 times that of the single-dose intramuscular injection group; followed by the high-dose nebulized inhalation group, which was around 8 times that of the single-dose intramuscular injection group. The euvirus neutralizing antibody level of the low- and medium-dose nebulized inhalation groups were comparable and was 2 times that of the intramuscular injection group. The mixed group and high-dose nebulized inhalation group had similar serum IgA antibody levels, which were on average higher than the low- and medium-dose nebulized inhalation groups.

An analysis of cellular immunity levels in the phase I trial was carried out. Results showed that effective cellular immunity could be generated 14 days after the first dose in various groups and higher level of cellular immunity could be induced 14 days after the second dose. The IFN- γ seroconversion rate was 80% and above and inter-group differences were not significant.

Following a single medium dose of the investigational vaccine via nebulized inhalation or two low/medium doses via nebulized inhalation, the resulting antibody levels in subjects aged 18–59 years were generally comparable to those in subjects aged ≥ 60 years. However, following two high doses via nebulized inhalation or two doses via a mixed route, the resulting antibody levels in subjects aged 18–59 years were higher than those in subjects aged ≥ 60 years.

3.4.2 A Heterologous clinical study on nebulized inhalation

In August 2021, a single-center, randomized, open-label, parallel-controlled clinical study was carried out in Donghai County, Jiangsu to evaluate the safety and immunogenicity of different doses of recombinant COVID-19 vaccine (adenovirus type 5 vector) for inhalation in people aged 18 years and above.

A total of 420 subjects aged 18 years and above were required to be enrolled in this study. Eligible subjects who provided informed consent and passed screening were randomly assigned at a ratio of 1:1:1 to Heterologous low-dose booster immunization group (group A), Heterologous high-dose immunization group (group B), and routine booster immunization group (group C). Subjects in groups A, B, and C must have completed prime immunization with 2 doses of the inactivated SARS-CoV-2 vaccine. Subjects enrolled in the study received a booster dose with either the inactivated SARS-CoV-2 vaccine or recombinant COVID-19 vaccine (adenovirus type 5 vector) for inhalation at 3–9 months after the aforementioned 2-dose vaccinations. The first 40 subjects in each group were included in the immunogenicity subgroup for immunogenicity monitoring.

Preliminary results:

Booster immunization showed good safety in all groups, and most ARs were of grade 1. The main local ARs in the nebulized inhalation group included dysphonia, dry mouth, oral mucositis, and pharyngeal swelling, while those in the intramuscular injection group (group C) included pain, swelling, and pruritus. The incidences of local ARs in the nebulized inhalation groups were lower than those in the intramuscular injection groups. Main systemic ARs reported by all groups were pyrexia, fatigue, and headache, and inter-group differences were not statistically significant.

Fourteen days after booster immunization, the incidences of overall solicited ARs in groups A, B, and C were 26 (18.57%), 33 (23.57%), and 54 (38.57%), respectively, with inter-group differences statistically significant ($P = 0.0004$); the incidences of grade 3 ARs were 2 (1.43%), 2 (1.43%), and 0 (0.00), with $P = 0.5524$.

The incidences of solicited local ARs were 9 (6.43%), 16 (11.43%), and 45 (32.14%), respectively, for groups A, B, and C, with statistically significant differences between groups ($P < 0.0001$). Among them, the incidences of grade 1 ARs were 8 (5.71%), 16 (11.43%), and 45 (32.14%), respectively, with statistically significant differences between groups ($P < 0.0001$). The incidence of grade 2 ARs were 1 (0.71%), 2 (1.43%), and 1 (0.71%), respectively ($P > 0.9999$). No grade 3 or greater solicited local ARs occurred.

The incidences of solicited systemic reactions in groups A, B, and C were 26 (18.57%), 27 (19.29%), and 21 (15.00%), respectively ($P = 0.6014$). Among them, the incidences of grade 1 ARs were 24 (17.14%), 25 (17.86%), and 21 (15.00%), respectively ($P = 0.8002$). The incidences of grade 2 ARs were 7 (5.00%), 6 (4.29%), and 2 (1.43%) ($P = 0.2341$). The incidences of grade 3 ARs were 2 (1.43%), 2 (1.43%), and 0 (0.00%) ($P = 0.5524$).

After the subjects received 1 booster dose of the recombinant COVID-19 vaccine (adenovirus type 5 vector) for inhalation within 3–9 months after 2 doses of inactivated vaccine, the induced levels of anti-SARS-CoV-2 S protein-RBD IgG antibodies and anti-SARS-CoV-2-specific neutralizing antibodies (euvirus) were obviously higher than those receiving 1 booster dose of the inactivated SARS-CoV-2 vaccine (intramuscular injection).

4 VACCINE OVERVIEW

Both recombinant COVID-19 vaccine (adenovirus type 5 vector) for inhalation and inactivated SARS-CoV-2 vaccine are administered in a 1-dose immunization procedure with an interval of \geq 6 months from the second dose of inactivated vaccine.

Investigational vaccine 1: inactivated COVID-19 vaccine (Vero cell) (hereinafter referred to as ICV)

Manufacturer: Sinovac Biotech Ltd./Beijing Institute of Biological Products Co., Ltd./Wuhan Institute of Biological Products Co., Ltd./Shenzhen Kangtai Biological Products Co., Ltd.

Strength: 0.5 mL/vial.

Dose: 0.5 mL

Administration route: Intramuscular injection in the lateral deltoid of the upper arm

Investigational vaccine 2: Recombinant COVID-19 vaccine (adenovirus type 5 vector) for inhalation (hereinafter referred to as Ad5-nCoV-IH)

Manufacturer: Beijing Institute of Biotechnology/CanSino Biologics Inc.

Strength: 1.5 mL/vial (1.5×10^{11} VP)

Dose: 0.1 mL (1×10^{10} VP)

Administration route: Oral inhalation using a nebulizer

Storage and transportation conditions:

Store and transport at 2–8 °C, away from light and freezing.

5. STUDY OBJECTIVES

5.1 Primary Objectives

1. To evaluate the safety of a booster dose of inactivated SARS-CoV-2 vaccine or recombinant COVID-19 vaccine (adenovirus type 5 vector) for inhalation.
2. To evaluate if the immunogenicity of a booster dose of recombinant COVID-19 vaccine (adenovirus type 5 vector) for inhalation is superior to that of inactivated COVID-19 vaccine.

5.2 Secondary Objective

To evaluate the persistence of immunogenicity after a booster dose of recombinant COVID-19 vaccine (adenovirus type 5 vector) for inhalation

6. STUDY DESIGN

Study design:

Multi-center, open-label clinical study, with a randomized, controlled immunogenicity group.

Randomization:

A total of 420 subjects in the immunogenicity group will be randomized in a 1:1 ratio to receive a booster dose of Ad5-nCoV-IH or ICV. Authorized investigators may assign each enrolled subject a study ID via the IWRS system. The investigators responsible for managing the vaccines will use the investigational vaccine that corresponds to the study ID and group allocation information.

Study design:

This study intends to enroll 10420 subjects aged 18 years and above, of which the population aged 60 years and above accounts for approximately $\geq 30\%$. This study includes a safety group and an immunogenicity group. The immunogenicity group also includes a cellular immunity group.

The immunogenicity group will include 420 subjects, and subjects ≥ 60 years should account for $\geq 30\%$ of the population. Eligible subjects who passed consultation and screening and provided informed consent will be randomized in a 1:1 ratio to receive a booster dose of either ICV or Ad5- nCoV-IH. Except for the Jiangsu CDC, the first 60 subjects from a single site of each of the other 5 centers will be included in the immunogenicity group. The first 120 subjects from a single site of the Jiangsu CDC will be included in the immunogenicity group, and the first 60 of these subjects will be included in the cellular immunity group.

Subjects assigned to receive an ICV booster dose will receive the vaccine from the same manufacturer as the two-dose prime immunization. All subjects will be issued diary cards on the day of vaccination and on Day 14 after vaccination for systematic safety observations. Venous blood and saliva samples will be collected from subjects in the immunogenicity group on the day of vaccination as well as 14 days, 28 days, 3 months, and 6 months after vaccination to test for serum antibody titers, serum IgA, and SIgA. Venous blood samples will be collected from subjects in the cellular immunity group on the day of vaccination and 14 days after vaccination to test for cellular immunity. All subjects are required to complete interviews on the day of vaccination as well as 14 and 28 days after vaccination. Subjects in the immunogenicity group are also required to complete 3- and 6-month follow-up visits. The remaining subjects may complete the 3- and 6-month visits via telephone follow-up. When about 2000 subjects (first stage) and 5000 subjects (second stage) are enrolled, the safety of all subjects in the early stage should be evaluated, and the enrollment schedule should be continued with the consent of PI. Enrollment will be suspended

or terminated immediately if a safety issue with vaccination is found to meet the suspension or termination criteria.

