Group	Vaccine/Dose	Study Center	Sample Size (subject)	Total (subject)															
Safety Group	Ad5-nCoV-IH 1.0×10^{10} VP (0.1 mL)	Jiangsu CDC	2500	10000															
		Chongqing CDC	1500																
		Shandong CDC	1500																
		Hunan CDC	1500																
		Anhui CDC	1500																

		Yunnan CDC	1500	
Immunogenicity Group	Ad5-nCoV-IH 1.0 × 10 ¹⁰ VP (0.1 mL) or ICV (0.5 mL)	Jiangsu CDC	120	420
		Chongqing CDC	60	
		Shandong CDC	60	
		Hunan CDC	60	
		Anhui CDC	60	
		Yunnan CDC	60	
Notes:				

 1. Recruited subjects must have completed prime immunization with 2 doses of inactivated vaccine. 2. The first 60 subjects (120 subjects for Jiangsu CDC) from a single site of each center will be included in the immunogenicity group. 3. The cellular immunity group will consist of the first 60 subjects in the immunogenicity group of a single site managed by Jiangsu CDC, who will undergo ICS testing on Day 0 and 14. 				
Randomization:				

The 420 subjects in the immunogenicity group will be randomized to receive a booster dose of Ad5-nCoV-IH or ICV in a 1:1 ratio. Authorized investigators may assign each enrolled subject a study ID via the IWRS system. The investigators responsible for managing the vaccines will use the investigational vaccine that corresponds to the study ID and group allocation information.
				
Study plan:				

This study plans to enroll 10,420 subjects aged 18 years and old. Subjects ≥ 60 years should account for ≥ 30% of the total population. Subjects must have completed prime immunization with 2 doses of inactivated vaccine. The booster immunization must be ≥ 6 months from the second dose. The safety group will include approximately 10,000 subjects, who will receive a booster dose of Ad5-nCoV-IH to determine the safety of the vaccine.
				

The immunogenicity group will include 420 subjects, and subjects ≥ 60 years should account for ≥ 30% of the population. Eligible subjects who passed consultation and screening and provided informed consent will be randomized in a 1:1 ratio to receive a booster dose of either ICV or Ad5-nCoV-IH. Except for the Jiangsu CDC, the first 60 subjects from a single site of each of the other 5 centers will be included in the immunogenicity group. The first 120 subjects from a single site of the Jiangsu CDC will be included in the immunogenicity group, and the first 60 of these subjects will be included in the cellular immunity group.
				

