6.3.2 Randomization numbering rules

Before vaccination during V1, each subject is assigned a unique randomization number by the study personnel on site via the IWRS system according to their enrollment sequence. Each randomization number corresponds to only one subject until the end of the study.

This study intends to enroll 10420 subjects aged 18 years and above, of which the population aged 60 years and above accounts for approximately $\geq 30\%$. A total of 6 study centers will be established (each study site may set up multiple vaccination sites). The 420 subjects in the immunogenicity group will be randomized to receive a booster dose of Ad5-nCoV-IH or inactivated SARS-CoV-2 vaccine in a 1:1 ratio. Rule for randomization numbers: Site number + 4-digit serial number, each site number will start with 0001. Jiangsu CDC + 0001–0060 will also be included in the cellular immunity subgroup. In the case of a subject dropping out after randomization but before vaccination, a substitute may be randomized. For example, if subject 0001 drops out before vaccination, the next enrolled subject will be the substitute with a randomization number of 10001; if the substitute also drops out before vaccination, the next enrolled subject will be a substitute with a randomization number of 20001; 9 substitutes is the maximum.

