8.5 Subject Randomization

The investigator will assign each subject in the immunogenicity group a unique randomization number via the IWRS system according to the arrival sequence, without skipping or saving numbers.

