8.11.2 Study hypotheses

This study will test a superiority hypothesis. The immunogenicity of 1 booster dose of Ad5 (adenovirus type 5 vector) vaccine for inhalation is non-inferior to that of 1 intramuscular injection of inactivated COVID-19 vaccine.

The superiority test will be carried out with the following hypothesis:

$$H_0 \text{ (null hypothesis): } T/C \leq 1$$

$$H_1 \text{ (alternative hypothesis): } T/C > 1$$

Superiority will be established when the lower limit of the one-sided 97.5% confidence interval of the GMT ratio ($\text{GMT}_{1 \text{ dose of inhalation}}/\text{GMT}_{1 \text{ dose of ICV}}$) of anti-SARS-CoV-2 neutralizing antibodies is greater than 1.

Testing strategy: When superiority is established in the overall population, superiority will also be tested in different age groups (18-59 years old, ≥ 60 years old). Age-stratified results will be used as supportive data. No adjustments will be made to the α .

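### The 30% minimum aged 60 or over in the immunogenicity group has no mechanism behind it: the group is filled first-come, with no age cap or stratum

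*Protocol*

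**What the plan says.** **Age minimum.** The synopsis study plan states "The immunogenicity group will include 420 subjects, and subjects ≥ 60 years should account for ≥ 30% of the population", and section 6 repeats it. The word used is should.

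**How the group is filled.** Section 6 says that "the first 60 subjects from a single site of each of the other 5 centers will be included in the immunogenicity group". For the sixth center, "The first 120 subjects from a single site of the Jiangsu CDC will be included in the immunogenicity group".

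**How numbers are issued.** Section 8.5 gives each subject in this group "a unique randomization number via the IWRS system according to the arrival sequence, without skipping or saving numbers". Section 6.3.2 builds the number as "Site number + 4-digit serial number, each site number will start with 0001", with no age component. When a randomized subject drops out before vaccination, the next subject enrolled is the substitute, and age is not matched.

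**Recruitment.** Section 8.1 places recruitment about two weeks before the first visit, at about 1.5 times the sample size, adjustable to circumstances. It sets no age mix.

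**Use of age in the analysis.** Section 8.11.2 says that, once superiority holds overall, "superiority will also be tested in different age groups" (18–59 and 60 or over). These results are labelled supportive, and alpha is not adjusted.

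**The concern.** The same group carries a minimum age composition and a filling rule that takes no account of age. A site that follows sections 6, 6.3.2 and 8.5 to the letter can finish its 60 subjects short of its share of older people, and the protocol does not say what should then happen.

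Two things are at stake. First, the group may miss a stated design target and have fewer subjects for the planned comparison in people aged 60 or over. Second, sites may each improvise a way to reach 30%, so that entry to the randomized group is managed by practices the protocol does not describe. The number format and the silence on stratification also suggest that the arm split among older subjects is left to chance, although results by age will be tested and reported.

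This goes beyond analysis detail. The protocol itself fixes who enters the group and in what order, and a statistical analysis plan cannot change enrolment order.

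**Working it through.** **1. The protocol's own sample size (section 6.2).** Inputs: GMT 16 and 32, standard deviation 9, one-sided alpha 0.025, power 85%, 183 per arm.

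- On the log scale, δ = ln(32/16) = 0.693. Reading 9 as a geometric SD gives σ = ln 9 = 2.197.
- n per arm = 2(1.960 + 1.036)² × (2.197/0.693)² ≈ 181. The noncentral-t version gives 182, and power at 183 per arm is 85.3%.
- On the raw scale (difference 16, SD 9) the formula gives 6 per arm, so the log reading is the one that fits.

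The stated 183 is reproduced to within 3% and is not in dispute. The same δ and σ are used in step 4.

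**2. Can first-come filling be relied on to reach the minimum?** The target is 0.30 × 420 = 126. The protocol gives no share of arrivals aged 60 or over, so that share p is an assumption, shown as a range. With arrivals taken as independent and unmanaged, X ~ Binomial(420, p):

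| Assumed p | P(X ≥ 126) |
|---|---|
| 20% | < 0.1% |
| 25% | 1.1% |
| 28% | 19% |
| 30% | 52% |
| 32% | 82% |
| 35% | 98.7% |
| 40% | > 99.9% |

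An arrival stream exactly on target meets the minimum only about half the time. Unmanaged filling becomes dependable only when the share is clearly above 30%.

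**3. Split of older subjects between arms without an age stratum.** With exactly 126 older subjects among 420 and 210 per arm, the number in one arm is hypergeometric:

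- mean = 126 × 210/420 = 63
- SD = √(126 × 0.25 × 294/419) = 4.7
- 95% range: 54 to 72

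**4. What that split costs.** Power in the older group, two-sample noncentral t, one-sided 0.025, noncentrality = δ / [σ√(1/n₁ + 1/n₂)]:

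| Older subjects by arm | Noncentrality | Power |
|---|---|---|
| 63 : 63 | 0.693/(2.197 × 0.178) = 1.77 | 42.0% |
| 54 : 72 | 0.693/(2.197 × 0.180) = 1.75 | 41.2% |
| 55 : 55 (30% of the 183 evaluable per arm) | 0.693/(2.197 × 0.191) = 1.65 | 37.4% |

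The imbalance costs under one percentage point. The older-group comparison is weak even at the full quota.

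**5. A quota under which both rules hold.** At least 18 of 60 older subjects at each of five sites and 36 of 120 at Jiangsu gives 5 × 18 + 36 = 126, exactly 30%. Equivalently, subjects aged 18–59 are capped at 42 per site and 84 at Jiangsu.

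**The case against.** **The rules are not incompatible.** A reader might infer that section 8.5 forbids any management of age mix, so that the quota cannot be met without breaking a rule. The text does not support that. Section 8.5 governs how randomization numbers are issued, not who is invited or when. Under section 8.1 a site could schedule enough older volunteers for its first sessions and then number everyone in arrival order, skipping nothing. This objection stands in full: the gap is an unstated mechanism.

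**The probabilities depend on the assumed share.** They run from 1.1% at 25% to 98.7% at 35%, and they assume no scheduling. They do not show that a miss is likely, only that the minimum is not assured unless arrivals run clearly above it or are managed. This also stands.

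**Randomization without age strata is not a flaw in validity.** A reader might infer bias in the comparison between arms. There is none: 1:1 randomization is unbiased whatever the age mix, and choosing whom to invite precedes allocation. The protocol also does not say that age strata are absent. It is silent, and a randomization specification could add them, although a single arrival-order series per site does not describe such a scheme.

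**The age tests are not confirmatory.** Section 8.11.2 calls them supportive and places them after overall superiority. The primary comparison in all 420 subjects is untouched.

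What remains is that the protocol states a composition target, fixes a filling rule that can miss it, and provides nothing to link the two.

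**Conclusion.** The point holds as an operational gap worth closing, with modest consequences. Following the stated filling rule can miss the stated 30% minimum, and no provision prevents or corrects this. How often it would be missed cannot be known from the protocol. Under independent, unmanaged arrivals the chance of success is about even when 30% of arrivals are aged 60 or over, and it changes steeply on either side.

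The effect on inference is small. There is no bias, the overall sample size reproduces, and chance imbalance of older subjects between arms costs about 0.8 percentage points of power (42.0% to 41.2%) in a supportive analysis. Those power figures rest on reading the protocol's standard deviation of 9 as a geometric SD and on the same twofold GMT ratio applying in older subjects.

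The case for change is that the remedy is cheap and makes the enrolment rule deliver what the protocol asks for.

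**What to change.** **Changes**

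- In the IWRS, cap subjects aged 18–59 at each immunogenicity site at 42 of 60 (84 of 120 at Jiangsu), leaving the remaining places for subjects aged 60 or over.
- In the synopsis and section 6, replace the first-60 and first-120 wording with the first eligible subjects within each age stratum, up to the site's cap.
- Randomize 1:1 by age group (18–59, 60 or over), with varying block sizes not disclosed to sites.
- Include age group in the primary log-titer model. Section 8.11.4.3.1 currently names a t test.
- Align the numbering and substitution rules in sections 6.3.2 and 8.5, so that a substitute comes from the same age stratum. Also align the definition of the cellular immunity group as Jiangsu 0001–0060 in sections 6.3.2 and 8.4, which presumes a single series.

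**Cost**

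The total of 420, the 1:1 ratio and the overall power are unchanged. The work is an IWRS setting and rewording in several sections. Sites with few older volunteers may fill more slowly. If strata are also formed within site, the older stratum holds only 18 subjects at most sites. In an open-label trial, short fixed blocks in so small a stratum would make the next allocation easier to guess, which is why block sizes should vary and stay undisclosed.
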